2.4.8. Neuroimaging

MRI scanning takes place on an FDA-approved 3T Skyra scanner (Siemens/Erlangen/Germany). We perform whole-brain functional fMRI using a gradient-echo EPI pulse sequence (33 contiguous oblique-axial slices angled 30° from the AC-PC axis, 4 mm thick, TR/TE = 2000/30 ms, flip angle = 90°, FOV = 200x200 mm, 120 total images per run).

- Food cue paradigm [42] – before (fasted state) and after (fed state) a standardized meal (see 2.4.6.): Participants view 100 high-calorie food stimuli (50% sweet/50% savory), 100 low-calorie food stimuli, 100 non-food object stimuli, and 100 fixation stimuli in a block design (5 runs, 4 minutes/run, 3 seconds/stimulus, 5 images/block, 16 blocks/run, images presented only once). Participants also rate a selection of food stimuli on valence and caloric content. The primary variable of interest is brain activation to high-calorie food stimuli compared to non-food stimuli.
- Stop-Signal Task (SST) [45,46] – fasted state: Participants are instructed to manually respond to visual go signals (circles) as fast and accurately as possible (within 3 seconds) but withhold their response when a stop signal (X) appears (25% of all trials, randomly selected, stop-signal delay following staircase-tracking algorithm). Trials are presented in a block design [64

trials/block, 3 blocks] following task practice outside the scanner. The primary variable of interest is brain activation to successful compared to failed response inhibition.

In addition to functional tasks, we acquire structural T1-weighted MRI images (MPRAGE sequence) for co-registration between structural and functional datasets. On a subset of participants (for whom scanning time allows), the Multi-Source Interference Task (an fMRI task reliably activating the cognitive control network involved in inhibiting task interference) [47], multi-echo T2-weighted MRI images, diffusion-weighted images, and resting state fMRI EPI images are acquired for further exploratory investigation of cognitive control, hypothalamic gliosis, white matter tractography, and functional connectivity.

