- Aim 1 – Determine oxytocin effects on weight, REE, and body composition: We hypothesize that 8-week intranasal oxytocin compared to placebo (a) reduces body weight, (b) increases REE (adjusted for lean/fat free mass), and (c) reduces total body, visceral, and liver fat in adults with obesity.
- Aim 2 – Determine oxytocin effects on caloric intake and underlying neural pathways (fMRI): We hypothesize that intranasal oxytocin compared to placebo reduces caloric intake at a test meal (independent of weight change), mediated by (a) reduced activation (in fasted and fed states) of reward-related food motivation (VTA, OFC, anterior insula) and homeostatic (hypothalamus) brain regions during a visual food stimuli paradigm and (b) increased impulse control indicated by increased activation (fasted state) of cognitive control-related brain regions (dlPFC, dACC, anterior portion of supplementary motor cortex/preSMA) during a validated task requiring the engagement of cognitive control to suppress impulsive responses.

The study is conducted under an Investigational New Drug application cleared by the U.S. Food and Drug Administration at a single study site, and the institutional review board approved the study protocol.

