2.5.2. Analysis of neuroimaging data

fMRI data will be analyzed using Statistical Parametric Mapping software running under the MATLAB® environment (SPM12) [52]. Preprocessing steps will include realignment and geometric unwarping using magnitude and phase images from the field map, slice-time correction, echo planar (EPI) co-registration to the participant's segmented, skull-stripped, bias-corrected T1-weighted image, normalization to Montreal Neurological Institute space with resampling to 2 mm isotropic using 4th degree B-spline interpolation, and smoothing with a 6 mm isotropic full width at half-maximum Gaussian kernel. Each run of EPI data will be evaluated for motion: (a) the degree of linear movement will be assessed and classified (threshold = 3 mm linear movement in orthogonal planes), and (b) the ART toolbox (Artifact Detection Tools; www.nitrc.org/projects/artifact_detect) will be used to detect outlier volumes based on image intensity relative to the global mean image (threshold = 3.5xSD) and motion (threshold = 0.8 mm, measured as scan-to-scan movement). Individual runs will be excluded if they show either (a) >3 mm linear movement and >10% outliers, or (b) >20% outliers.

For subject-level analyses, a general linear model (GLM) either with regressors of high-calorie foods, low-calorie foods, and objects (food cue paradigm) or with regressors of successful stop trials and failed stop trials (SST) will be specified. Regressors will be placed at the onset of each condition within a block, convolved with the canonical hemodynamic response function. Global mean signal and motion outliers will be entered as nuisance regressors. Following GLM estimation, the primary contrast (high-calorie foods versus objects, successful versus failed stop trials) will be computed at the single-subject level to estimate condition effects at every voxel, separately for each session (fasted/fed). For subsequent group-level analysis, we will use a factorial design with baseline versus 4-week contrasts to examine changes in brain activation

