following oxytocin treatment in a-priori defined regions of interest (ROIs, food cue paradigm: VTA, OFC, anterior insula; SST: dlPFC, dACC, preSMA). For mediation analyses, beta values will be extracted from subject-level contrast images for clusters within a-priori ROIs that meet family-wise error rate correction ($p < 0.05$) using Marsbar software [53]. We will also analyze activation in additional reward-related food motivation and impulse control-related brain regions and the whole brain (applying α -error correction procedures). Moreover, we will examine activation in the hypothalamus as a brain region responsible for energy homeostasis.

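### The only Stop-Signal Task contrast specified, successful minus failed stops, cannot by itself show the increased activation that Aim 2(b) predicts; its two components should be reported beside it

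*Combined protocol and SAP*

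**What the plan says.** Section 2.1, Aim 2(b), states the hypothesis as a direction of activation: "increased impulse control indicated by increased activation (fasted state) of cognitive control-related brain regions". The regions named are dlPFC, dACC and preSMA.

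Section 2.4.8 describes the task ("25% of all trials, randomly selected, stop-signal delay following staircase-tracking algorithm") and defines its outcome: "The primary variable of interest is brain activation to successful compared to failed response inhibition".

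Section 2.5.2 sets up the subject-level model "with regressors of successful stop trials and failed stop trials (SST) will be specified". No go-trial regressor is named. It then says that "the primary contrast (high-calorie foods versus objects, successful versus failed stop trials) will be computed at the single-subject level". At group level, "we will use a factorial design with baseline versus 4-week contrasts to examine changes in brain activation". For mediation, "beta values will be extracted from subject-level contrast images for clusters within a-priori ROIs", limited to clusters that survive family-wise error correction. Section 2.5.3 uses these week-4 changes as possible mediators of the week-6 change in test-meal intake.

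The additional imaging analyses in section 2.5.2 widen the anatomy, not the set of task contrasts: "We will also analyze activation in additional reward-related food motivation and impulse control-related brain regions and the whole brain". The Figure 3 note that allows further contrasts concerns study endpoints and their assessment time points.

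**The concern.** The hypothesis is about a level of activation, but the measured quantity is a difference between two conditions. Both conditions present the stop signal and call for the response to be withheld. An oxytocin effect on the attempt to stop could therefore appear on both, and the subtraction removes whatever they share. The subtraction also cannot tell a rise on successful stops from a fall on failed stops.

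Two misreadings could follow. A real rise common to all stop trials could be reported as no effect. A fall confined to failed stops could be reported as support for Aim 2(b). Either would carry into the mediation analysis for the three control regions.

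Nothing else that the plan specifies would settle which case occurred. No behavioural outcome from this task is named. The Multi-Source Interference Task is optional, run where scanning time allows, and exploratory.

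**Working it through.** The plan gives no power or precision figure for this contrast, so there is no stated figure to reproduce. The check is contrast algebra.

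**Definitions.** S and F are the betas for successful and failed stops. dS and dF are the oxytocin-minus-placebo differences in their change from baseline to week 4.

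**Formula.** Within each arm, the change in the contrast is (S at week 4 − F at week 4) − (S at baseline − F at baseline). The between-arm difference in that change is dS − dF, whatever the baseline values.

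**Illustrative shifts** (assumed sizes, with no change on go trials):

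| Pattern on oxytocin | dS | dF | Successful minus failed (dS − dF) | Successful-stop component (dS) |
|---|---|---|---|---|
| Equal rise on all stops | +0.3 | +0.3 | 0 | +0.3 |
| Rise on successful stops only | +0.3 | 0 | +0.3 | +0.3 |
| Fall on failed stops only | 0 | −0.3 | +0.3 | 0 |
| Fall on both, larger on failed | −0.1 | −0.4 | +0.3 | −0.1 |
| Rise on both, larger on failed | +0.2 | +0.4 | −0.2 | +0.2 |

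Rows 2 to 4 give the same planned result, but activation on successful stops rises in only one of them. In row 5 activation rises on both trial types and the planned contrast is negative.

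**Check by model fit.** A noise-free least-squares fit used 192 trials, regressors for the two stop types, go trials as the implicit baseline, and assumed starting betas S = 1.0 and F = 0.8. The contrast starts at 1.0 − 0.8 = 0.2.
- Equal rise: 1.3 − 1.1 = 0.2, unchanged.
- Rise on successful stops only: 1.3 − 0.8 = 0.5.
- Fall on failed stops only: 1.0 − 0.5 = 0.5.

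**Trial counts (section 2.4.8).** 64 × 3 = 192 trials. Stop trials are 25% of these, 48, which leaves 144 go trials. The staircase's target success rate is not stated. At an assumed 50% the split is 24 successful and 24 failed; at 40% to 60% it runs from about 19/29 to 29/19.

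**Precision, first-level error only, at the assumed 50%.** The variance factor for successful minus failed is 1/24 + 1/24 = 0.083. For successful minus go it is 1/24 + 1/144 = 0.049. The standard-error ratio is √(0.0486/0.0833) = 0.764, about 24% smaller. Between-participant variance dilutes this. If that variance is the same for both contrasts and equals 0.0833, the ratio is √(0.1319/0.1667) = 0.89, about 11% smaller. If it is twice as large, the ratio is √(0.2153/0.25) = 0.93, about 7% smaller. The point does not rest on precision.

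**The case against.** **The contrast is defensible.** Aim 2(b) concerns control used to suppress impulsive responses, and successful minus failed isolates success at that. Because both trial types contain the rare stop cue, the subtraction also removes the response to the cue. This stands, and it is why the contrast should remain primary.

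**Any difference has this property.** Successful minus go rises if go activation falls. It also retains the rare cue and the difference between responding and withholding. This stands too. A reader might infer that a stop-minus-go contrast should decide Aim 2(b) and supply the main mediator. The documents do not support that: it would exchange one imperfect contrast for another, after all 61 participants were randomized.

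**The plan does not say that this is the only contrast.** Correct. It says primary and excludes no others. But it names none, so any component analysis would be chosen later.

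**Full cancellation is a special case.** Correct. It requires equal rises on both trial types; with unequal rises the difference remains. The documents do not say how far the two trial types share a response. A reader might infer that the contrast is bound to miss the hypothesised effect. It misses only the shared part.

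**The planned model already holds the components.** If go trials form the implicit baseline, the two stop betas are already estimated largely against them. This stands in part. It makes the remedy cheap, but the plan does not say that the components will be reported or how they bear on the claim.

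**Conclusion.** The point holds in limited form. As specified, a positive change in the primary contrast shows that the success–failure difference has widened. It does not show that activation rose, which is what Aim 2(b) says. The algebra is exact for any beta values. How often the misleading patterns would arise cannot be judged from the documents, and the table's reading of the successful-stop component assumes no change on go trials.

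The consequence is confined to Aim 2(b) and the cognitive-control part of an exploratory mediation analysis. The weight endpoint and the key secondary endpoints in section 2.3 are unaffected. Two stronger readings should be avoided: that the contrast is invalid, and that it should be replaced because it is noisier. The 24% figure covers first-level error only, under an assumed 50% success rate, and has no bearing on validity.

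This is a cheap improvement, worth making before the imaging analysis is run.

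**What to change.** In section 2.5.2:
- Keep successful minus failed stops as the primary contrast and as the main source of mediator values.
- Add a go-trial regressor to the Stop-Signal Task model.
- Compute successful-stop minus go and failed-stop minus go in the same a-priori regions at baseline and week 4. Report both by arm beside the primary contrast, within the same error correction.
- State the claim rule: a positive change in successful minus failed is described as increased activation under Aim 2(b) only if the successful-stop component itself rises on oxytocin versus placebo. Otherwise it is described as a change in the success–failure difference.

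In section 2.5.3, repeat the cognitive-control mediation of caloric intake with the successful-stop component, as a sensitivity analysis.

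The cost is SAP wording, one regressor and two contrasts on scans already in the plan. The downsides are two more contrasts to correct for, and the rare-cue and motor differences carried by stop-minus-go. For that reason the components supplement the primary contrast and do not replace it.

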2.4.9. Psychological, behavioral, and quality of life assessments

We use self-report questionnaires and behavioral tasks to assess obesity-related psychological aspects and behaviors that might also be affected by oxytocin administration, including physical activity, appetite and eating behavior and attitudes [11], reward processing and food motivation [29,30,48], impulse control, socioemotional functioning [49,50], and mood and anxiety symptoms [51]. Quality of life will also be evaluated. See Table 2 for details.

2.5. Biostatistical considerations

2.5.1. Sample size and statistical power

Sixty-one participants were randomized to obtain evaluable data for at least 50 participants completing the 8-week treatment period. We conducted power and sample size calculations using 2-sample t-tests at a 2-tailed significance level of $\alpha = 0.05$. The primary endpoint of this study is percent change in body weight from baseline following 8-week intranasal oxytocin treatment compared to placebo; with 25 participants per arm, we have 80% power to detect a between-group (oxytocin versus placebo) mean difference in weight loss of ≥ 3.2 kg, based on a reported

standard deviation for the between-group difference in weight loss of approximately 4 kg in a pilot study of 8-week intranasal oxytocin administration in adults with obesity [35].

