2.3. Study and safety endpoints

The primary endpoint is percent change in body weight from baseline following 8-week intranasal oxytocin compared to placebo. Key secondary endpoints include change from baseline to end of treatment in (a) REE (adjusted for lean mass), (b) body composition (total body, visceral, and liver fat mass), and (c) caloric intake (adjusted for weight) following 8-week intranasal oxytocin compared to placebo.

Other secondary endpoints include change in metabolic profile (e.g., insulin sensitivity, lipid panel, high-sensitivity C-reactive protein [hsCRP] at 8 weeks; fat metabolism at 2 weeks), behavior (e.g., eating behavior, reward-related food motivation, impulse control, social emotional functioning, symptoms of disordered eating, depression, and anxiety), and quality of life between baseline and 8-week intranasal oxytocin treatment compared to placebo (Table 2).

We systematically assess safety and treatment tolerability throughout the study (Table 2), with a final safety visit 6 weeks after treatment completion and additional visits if needed (e.g., early termination). We categorize severity of adverse events according to the Common Terminology Criteria for Adverse Events (CTCAE, v5.0) [37] and evaluate expectedness of adverse events and relationship to study drug and procedures.

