^tReading the Mind in the Eyes Test (behavioral task) assessing theory of mind [75].

^uState Adult Attachment Measure (self-report) capturing attachment insecurity [76].

^vToronto Alexithymia Scale (self-report) measuring the ability to describe and identify emotions [77].

BL, baseline visit; T, Treatment; W, week of visit; HR, heart rate; MMSE, Mini-Mental Status Exam; CBC, complete blood count; TSH, thyroid stimulating hormone; CMP, comprehensive metabolic panel (including liver [alanine/aspartate transaminase] and renal [creatinine] function tests, electrolytes [potassium, sodium], and glucose); HbA1c, hemoglobin A1c; EKG, electrocardiogram; M.I.N.I., Mini-International Neuropsychiatric Interview; hCG, human chorionic gonadotropin; REE, resting energy expenditure; DXA, dual-energy X-ray absorptiometry; MRI, magnetic resonance imaging; 1H-MRS, magnetic resonance spectroscopy; hsCRP, high-sensitivity C-reactive protein; VTA, ventral tegmental area; OFC, orbitofrontal cortex; dlPFC, dorsolateral prefrontal cortex; dACC, dorsal anterior cingulate cortex; preSMA, anterior portion of the supplementary motor cortex; BDI, Beck Depression Inventory; STAI, State Trait Anxiety Inventory; SF-36, 36-Item Short Form Survey.

Table 3. Characteristics of the randomized participants at baseline (BL1 visit).

Characteristic	Mean (SD) or N (%)
Demographics	
N randomized	61
Biological sex: F M	33 (54.10%) 28 (45.90%)
Age (years)	33.58 (6.22)
Race	
• Asian	6 (9.84%)
• Black	13 (21.31%)
• White	38 (62.30%)
• Other/More than one race	3 (4.92%)
• Asked but unknown	1 (1.64%)
Ethnicity	
• Hispanic/Latino ethnic group	12 (19.67%)
Clinical characteristics	
BMI (kg/m ²) [F M]	37.02 (4.93) [37.77 (4.92) 36.13 (4.87)]
BMI distribution (kg/m ²)	
• ≥30 to <35 [F M]	24 (39.34%) [8 16]
• ≥35 to <40 [F M]	21 (34.43%) [15 6]
• ≥40 [F M]	16 (26.23%) [10 6]

Abbreviations: F, female; M, male; BMI, body mass index.

Figures

[figure not shown]

Figure 1. Proposed model of oxytocin effects on eating behavior and metabolism leading to weight loss.

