Intranasal oxytocin may reduce body weight via multiple complementary mechanisms. Oxytocin may suppress caloric intake via reduced activation of reward and homeostatic brain regions and increased activation of cognitive control brain regions. Oxytocin reduces inflammation, which in turn may reduce appetite and increase energy expenditure. Oxytocin increases thermogenesis and energy expenditure. These effects lead to lipolysis, fat oxidation, and reduced fat mass, ultimately resulting in weight loss.

[figure not shown]

Figure 2. Study design.

Abbreviations: IU, international unit; REE, resting energy expenditure; BL, baseline visit; W, week of visit.

Order of analyses

Randomized, double-blind, placebo-controlled clinical trial

Participants: F/M, 18-45 years, BMI ≥ 30 kg/m²

Randomization at BL: 1 : 1 oxytocin : placebo

Stratification: Biological sex, BMI

1 – Endpoints

Variable	Use/Objective	Variable type	Statistical model	Methods for missing data
Change(%) in body weight (Δ_{W8-BL})	Primary endpoint	Continuous	Mixed-model regression for repeated measurements (MMRM), adjustment for multiple comparisons as appropriate via approach of Hothorn, Bretz, and Westfall	Modified intention-to-treat approach (mITT), Multiple imputation (MI) where applicable
REE (adjusted for lean mass) (Δ_{W8-BL})	Key secondary endpoint	Continuous		
Total body, visceral, and liver fat mass (Δ_{W8-BL})	Key secondary endpoint	Continuous		
Caloric intake (Δ_{W6-BL} , Δ_{W8-BL})	Key secondary endpoint	Continuous		
Metabolic profile (Δ_{W8-BL})	Secondary endpoint	Continuous		
Psychological, behavioral and quality of life assessments	Secondary endpoint	Continuous	Descriptive statistics	
Vital signs, QTc on EKG, %IBW, BMI, waist-to-hip ratio	Vital signs, EKG, anthropometrics	Continuous		
Age, biological sex, race, ethnicity, coexisting conditions, medication	Demographic and clinical variables	Continuous/Categorical		

2 – Mediators

Mediator variable	Dependent variable	Independent variable	Statistical model
Brain activation (Δ_{W4-BL}): food reward, homeostatic and cognitive control regions	Caloric intake (Δ_{W6-BL})	Treatment (oxytocin vs. placebo)	Regression-based mediation analysis
Caloric intake (Δ_{W6-BL})	Change(%) in body weight (Δ_{W8-BL})	Treatment	
REE (Δ_{W6-BL})	Change(%) in body weight (Δ_{W8-BL})	Treatment	

3 – Safety and Compliance (all study time points)

Variable	Use/Objective	Variable type	Statistical model

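### Does stating power in kilograms, when the primary endpoint is percent weight change, leave the trial's sizing in doubt?

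*Combined protocol and SAP*

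**What the plan says.** Section 2.3 sets the endpoint: "The primary endpoint is percent change in body weight from baseline following 8-week intranasal oxytocin compared to placebo". Section 2.5.1 repeats it, and the main endpoint table in Figure 3 lists "Change(%) in body weight" from baseline to week 8 as primary.

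Section 2.5.1 also holds the only power statement. It specifies the method ("We conducted power and sample size calculations using 2-sample t-tests", two-tailed at 0.05), 25 per arm and 80% power, and gives the detectable effect as a "mean difference in weight loss of ≥ 3.2 kg". The variability comes from the 8-week pilot study and is described as a "standard deviation for the between-group difference in weight loss of approximately 4 kg".

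No section gives a standard deviation of percent change, a target percent difference or a conversion from kilograms. Table 3 reports BMI but neither weight nor height.

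**The concern.** Two things look wrong. First, the trial will be judged on a percent difference but was sized on a kilogram difference. The two scales are interchangeable only if everyone weighs about the same. Here BMI runs from 30 to above 40, so the standard deviation of percent change depends on the spread of baseline weight and on how weight change relates to it. A reader facing a null or borderline percent result cannot find in the plan what percent difference the trial could detect.

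Second, a two-sample t-test needs the standard deviation of individual weight change within an arm, whereas the text attaches the 4 kg to the between-group difference. If that were literally the quantity used, the stated power would be wrong, possibly by a lot. At stake would be whether 25 per arm is enough for the primary endpoint.

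**Working it through.** **Inputs from the plan.** Section 2.5.1: n = 25 per arm, difference 3.2 kg, SD 4 kg, two-sided alpha 0.05, power 80%. Sections 1 and 2.6: the pilot had 20 adults, 9 on oxytocin, hence 11 on placebo by subtraction. Table 3: 33 women with mean BMI 37.77 and 28 men with mean BMI 36.13.

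**Step 1: reproduce the plan's figure, with 4 kg as the within-arm SD.**
- Noncentrality = 3.2 / (4 × √(2/25)) = 2.83, with 48 degrees of freedom and critical t = 2.011.
- Power = 79.1% (noncentral t), or 80.7% by the normal approximation.
- Difference detectable with 80% power = 0.8087 × 4 = 3.23 kg (noncentral t), or 3.17 kg (normal).

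Both round to the stated 3.2 kg.

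**Step 2: take the label literally.**
- As the SD of a difference between two individuals: within-arm SD = 4/√2 = 2.83 kg, power 97.5%, detectable difference 2.29 kg.
- As the standard error of the pilot's mean difference: within-arm SD = 4/√(1/9 + 1/11) = 8.90 kg, power 23.8%, detectable difference 7.2 kg.

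Neither gives 80% at 3.2 kg. Of the readings tried, only the within-arm SD does, so the calculation used the quantity a t-test needs and the fault lies in the description.

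**Step 3: convert to percent by mean weight.** Heights are not in the documents. Assume women 1.60 to 1.66 m and men 1.73 to 1.80 m. Mean weight = (33 × 37.77 × hF² + 28 × 36.13 × hM²)/61:

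| Assumed heights, women / men (m) | Mean weight (kg) | 3.2 kg as % of weight |
|---|---|---|
| 1.60 / 1.73 | 101.9 | 3.14 |
| 1.63 / 1.765 | 106.0 | 3.02 |
| 1.66 / 1.80 | 110.0 | 2.91 |

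Dividing the difference and the SD by the same weight leaves their ratio, and so the power, at 79.1%.

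**Step 4: allow for the spread of weight.** Further assumptions: baseline weight SD 14 to 22 kg, mean change 0 to −3.2 kg, correlation of change with baseline weight −0.5 to 0.5, SD of change 4 kg. Simulating 100 × change/baseline (500,000 draws per case, baseline floored at 70 kg) gives the percent SD. Multiplying by 0.8087 gives the detectable difference.

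| Case | Percent SD (points) | Detectable at 80% (points) | Power for 3.0 points |
|---|---|---|---|
| Lowest (110 kg, SD 14, change −3.2, r −0.5) | 3.58 | 2.9 | 83% |
| Central (106 kg, SD 18, change −1.6, r 0) | 3.95 | 3.2 | 75% |
| Highest (102 kg, SD 22, change −3.2, r 0.5) | 4.56 | 3.7 | 63% |

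**Step 5: set this against the analysis set.** Figures for 25 per arm assume 50 analysed. Section 2.5.3 admits to the efficacy analysis every randomised participant with data at the second baseline visit and the first on-treatment visit, so the number can exceed 50. If all 61 contributed week 8 data (30 and 31 per arm), power for 3.2 kg with SD 4 kg would be 86.7%.

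**The case for a change.** The strongest case for a correction is that it is cheap and would help interpretation. The literal readings of the label give power from 24% to 97%, the percent SD cannot be recovered from the document, and the Discussion describes the trial as carefully powered. A relabelled SD and one sentence in percent would let a reader judge a null result.

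Part of this stands. The units do differ from the endpoint, the label is imprecise, and in the central case power for 3.0 points is 75%, somewhat under the nominal 80%.

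It does not support a change, for four reasons.
- The spread from 24% to 97% belongs to readings that the plan's own figure rules out.
- What the pilot study reported cannot be checked from the documents, so a firm relabelling would itself be an inference.
- A percent SD built from the weights of people already randomised would be a retrospective conversion. It would not show what the trial was sized to detect, because that target was set in kilograms. A general statement that the detectable difference is 0.81 times the SD is t-test algebra and says nothing specific to this trial.
- An unadjusted t-test is a planning approximation on either scale. The primary analysis is a mixed model adjusted for baseline value, sex and BMI, and the confidence interval it yields on the percent scale will show directly which differences the data exclude.

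**Conclusion.** The mismatch is real but is a reporting gap with a loosely worded label. It is neither an arithmetic error nor a demonstrated loss of power. The kilogram figure reproduces (79.1% power at 3.2 kg, 3.23 kg detectable at 80%) with 4 kg as the within-arm SD. On the percent scale the detectable difference is about 2.9 to 3.7 points, and power for 3.0 points is about 83% to 63%. These ranges depend on assumed heights, weight spread, mean change and correlation, none of which the documents give, so they do not establish that the trial falls short.

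No decision turns on the point. Randomisation is complete at 61, and the endpoint and its model are defined in percent in Sections 2.3 and 2.5.3 and Figure 3. An analyst following the plan would compute the same estimate, interval and test with or without an added percent figure. No change is needed.
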